8.1.2.2. Neurotoxicity

CAR T_{eff} cell therapy has been shown to be associated with neurological toxicities, also known as CAR T-Cell Related Encephalopathy (CRES) or Immune effector Cell-Associated Neurotoxicity Syndrome (ICANS) that may correlate with high cytokine levels. The risk of neurotoxicity with SBT777101 treatment is unknown given the difference in mechanism of action from CAR T_{eff} therapies used in the oncology setting. However, CRES was not observed in studies of polyclonal T_{regs} in patients with autoimmune indications (see SBT777101 Investigator Brochure).

Neurotoxicity can be characterized by the following signs and symptoms (Siegler and Kenderian, 2020):

- Confusion
- Aphasia
- Tremor
- Word finding difficulty
- Lethargy

- Obtundation
- Stupor
- Seizures
- Coma
- Myoclonus

In general, onset of neurologic symptoms has been seen to begin five to seven days after CAR Teff therapy administration.

Subjects receiving SBT777101 should be monitored closely for signs and symptoms of neurotoxicity. Management of neurologic toxicity should occur according to site protocols or standard clinical practice.

See Appendix G for guidance on grading neurotoxicity adverse events according to the ICANS scale.

8.1.2.3. Malignancies

Risks of cell therapy using a lentivirus include insertional mutagenesis. There have been no reports of long-term toxicities associated with retroviral vector-mediated gene transfer into mature T cells and an insertion site analysis conducted for SBT777101 showed a polyclonal integration site profile with no dominant integration site (Milone and O'Doherty, 2018). Subjects will be monitored for 1 year in this study and longer term in a safety follow-up protocol as per current FDA guidelines.

8.2. Safety Parameters and Definitions

Safety assessments will consist of monitoring and recording adverse events, including serious adverse events, performing protocol-specified safety laboratory assessments, measuring

protocol-specified vital signs, and conducting other protocol-specified tests that are deemed critical to the safety evaluation of the study.

Certain types of events require immediate reporting to the Sponsor, as outlined in Section 8.2.2.

8.2.1. Adverse Events (AEs) Serious Adverse Events (SAEs) and Other Safety Reporting

The definitions of adverse events (AEs) and serious adverse events (SAEs) can be found in Appendix E.

AEs will be reported by the subject.

The Investigator and any qualified designees are responsible for detecting, documenting, and recording events that meet the definition of an AE or SAE and remain responsible for following up AEs that are serious or considered related to the study intervention or study procedures.

The method of recording, evaluating, and assessing causality of AEs and SAEs and the procedures for completing and transmitting SAE reports are provided in Appendix E.

8.2.2. Time Period and Frequency for Collecting AE and SAE Information

All SAEs plus any AE that is the result of a protocol specified procedure or intervention will be collected from the signing of the ICF until study drug administration.

All AEs will be collected from the time of first study drug administration until the final safety follow-up visit.

Medical occurrences that begin before study drug administration but after obtaining informed consent will be recorded as medical history/current medical conditions, not as AEs.

All SAEs will be recorded and reported to the Sponsor or designee immediately and under no circumstance should this exceed 24 hours, as indicated in Appendix E. The Investigator will submit any updated SAE data to the Sponsor within 24 hours of it being available.

Investigators are not obligated to actively seek information on AEs or SAEs after conclusion of the study participation. However, if the Investigator learns of any SAE, including a death, at any time after a subject has been discharged from the study, and he/she considers the event to be reasonably related to the study intervention or study participation, the Investigator must promptly notify the Sponsor.

8.2.3. Method of Detecting AEs and SAEs

Care will be taken not to introduce bias when detecting AEs and/or SAEs. Open-ended and nonleading verbal questioning of the subject is the preferred method to inquire about AE occurrences.

8.2.4. Follow-Up of AEs and SAEs

After the initial AE/SAE report, the Investigator is required to proactively follow each subject at subsequent visits/contacts. All SAEs will be followed until resolution, stabilization, the event is otherwise explained, or the subject is lost to follow-up (as defined in Section 7.4.2). Further information on follow-up procedures is provided in Appendix E.

8.2.5. Regulatory Reporting Requirements for SAEs

- Prompt notification by the Investigator to the Sponsor of an SAE is essential so that legal obligations and ethical responsibilities towards the safety of subjects and the safety of a study intervention under clinical investigation are met.
- The Sponsor has a legal responsibility to notify both the local regulatory authority and other regulatory agencies about the safety of a study intervention under clinical investigation. The Sponsor will comply with country-specific regulatory requirements relating to safety reporting to the regulatory authority, institutional review boards (IRBs)/independent ethics committees (IECs), and investigators.
- An Investigator who receives an Investigator safety report describing an SAE or other specific safety information (e.g., summary or listing of SAEs) from the Sponsor will review and then file it along with the IB and will notify the IRB/IEC, if appropriate according to local requirements.
- Investigator safety reports must be prepared for suspected unexpected serious adverse reactions (SUSARs) according to local regulatory requirements and Sponsor policy and forwarded to investigators as necessary.

8.2.6. Pregnancy

- Details of all pregnancies in female subjects will be collected after the start of study intervention and until completion of final safety follow-up visit.
- If a pregnancy is reported, the Investigator will record pregnancy information on the appropriate form and submit it to the Sponsor within 24 hours of learning of the female subject or female partner of male subject (after obtaining the necessary signed informed consent from the female partner) pregnancy.
- While pregnancy itself is not considered to be an AE or SAE, any pregnancy complication or elective termination of a pregnancy for medical reasons will be reported as an AE or SAE.
- Abnormal pregnancy outcomes (e.g., spontaneous abortion, fetal death, stillbirth, congenital anomalies, ectopic pregnancy) are considered SAEs and will be reported as such.
- The subject will be followed to determine the outcome of the pregnancy. The Investigator will collect follow-up information on the subject/pregnant female partner and the neonate and the information will be forwarded to the Sponsor.
- Any poststudy pregnancy-related SAE considered reasonably related to the study intervention by the Investigator will be reported to the Sponsor as described in Appendix E. While the Investigator is not obligated to actively seek this information in former study subjects/pregnant female partner, he or she may learn of an SAE through spontaneous reporting.

9. STATISTICAL CONSIDERATIONS

9.1. Determination of Sample Size

The sample size in this study was not selected based on statistical considerations but to determine preliminary safety, tolerability, PK, PD, and preliminary clinical activity of SBT777101 subjects with active RA.

This study will enroll up to 36 eligible adult subjects with RA. Up to 18 eligible adult subjects will be enrolled in escalation cohorts and an additional 18 subjects may be included in optional backfill cohorts.

9.2. Blinding and Randomization

This clinical study is open-label, and all subjects enrolled will be treated with SBT777101.

9.3. Analysis Datasets

The following populations will be considered in the analysis of data for this study.

- Safety population: All subjects who received any portion of an infusion of study drug will be included in the safety population. The safety population will be used for both the safety and efficacy analyses.
- PK/PD population: will include all subjects in the safety analysis set with the necessary pre- and post-dose measurement to provide interpretable results for the specific parameter of interest. Subjects will be excluded from the PK/PD analysis if they have protocol deviation or any important event that would affect the interpretation and integrity of the concentration data.

9.4. Endpoints

9.4.1. Primary Endpoint

To evaluate and characterize the safety and tolerability of SBT777101:

- Incidence, nature and severity of AEs
- Incidence and nature of DLTs
- Changes from baseline in clinical laboratory tests, 12-lead ECG parameters and targeted vital signs

9.4.2. Exploratory Endpoints

9.4.2.1. PK Endpoints

To assess and characterize SBT777101 pharamcokinetic profile in peripheral blood and synovium:

• The determination of PK parameters including but not limited to T_{max}, C_{max}, AUC₀₋₂₈, C_{last} by the evaluation of CAR transgene levels in peripheral blood

Presence and levels of SBT777101 in the synovial tissue and/or fluid

9.4.2.2. Mechanism of action and PD Endpoints

To assess and characterize SBT777101 mechanism of action and pharmacodynamic parameters in peripheral blood and the synovium:

- Levels of systemic markers of inflammation in peripheral blood including but not limited to TNFα, CRP, IL-6 pre-dose and following SBT777101 administration
- Levels of inflammatory cells and biomarkers in synovial tissue and/or synovial fluid pre-dose and following SBT777101 administration
- Change from baseline in phenotypic and molecular signatures in T cells and other immune subsets in peripheral blood and synovial tissue and/or fluid following SBT777101 administration

9.4.2.3. Immunogenicity Endpoints

To assess the immunogenicity of SBT777101:

- Presence of anti-drug antibodies in serum at baseline and following SBT777101 administration
- Detection of cellular immunogenicity pre-dose and following SBT777101 administration

9.4.2.4. Efficacy Endpoints

To assess the preliminary efficacy of SBT777101:

- ACR20, ACR50 and ACR70 response rates following SBT777101 administration
- DAS28 scores and change from baseline in DAS28 scores following SBT777101 administration

9.5. Data Handling Convention

Descriptive statistics on continuous data will include means, medians, Q1, Q3, standard deviations, and ranges. Categorical data will be summarized using frequency counts and percentages.

Laboratory data that are continuous in nature but are less than the lower limit of quantitation or above the upper limit of quantitation will be imputed to the value of the lower or upper limit plus or minus one significant digit, respectively (e.g., if the result of a continuous laboratory test is <10, a value of 9 will be assigned).

Missing data can have an impact upon the interpretation of the trial data. In general, values for missing data will not be imputed. However, a missing pre-treatment laboratory result would be treated as normal (e.g., no toxicity grade) for the laboratory abnormality summary.

All analyses and summaries will be presented by dose level and overall.

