7.2.6.4.1. Pharmacodynamic Biomarkers

Pharmacodynamic (PD) effects of SBT777101 will be evaluated by measurement of relevant inflammatory cytokines (including but not limited to: IL-1, IL-6, IL-10, IL-15, IL-17, TNF α and interferon-gamma (IFN γ)) and chemokines, as well as measurement of levels of C-reactive protein (CRP) and ACPA pre-dose and after dosing.

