7.3. Order of Study Assessments

The preferred order of assessments for study visits is as follows:

- Safety assessments (ECG must be performed first, followed by vital signs, where required)
- Demographics, medical history and concomitant medication review
- Clinical assessments (PROs must be performed prior to any interventional assessments including lab draws)
- Clinical laboratory tests
- Labs for RCL
- Labs for PK and immunogenicity
- Labs for PD
- Labs for exploratory biomarkers
- Study drug administration
- Synovial biopsy and/or synovial fluid collection and ultrasound evaluation of joints

Unscheduled safety assessments should take priority over any scheduled clinical or PK assessments.

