9.7.4. PK and Immunogenicity Analysis

SBT77701 CAR transgene level in peripheral blood and PK parameters will be listed and summarized using descriptive statistics. Relevant PK parameters (T_{max}, C_{max}, AUC₀₋₂₈, C_{last}) will be determined using standard non-compartmental methods.

Immunogenicity data will be listed by subject. The proportion of subjects with a positive anti-drug antibody result will be summarized over time and by dosing level. Proportion of subjects with at least one positive result post dosing will be summarized.

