APPENDIX B. SCHEDULE OF ASSESSMENTS: BASELINE AND SAFETY FOLLOW-UP PERIOD

	Safety Follow Up														UV	\mathbf{E}	
Study Week Study Day (visit window)	1					2	3 4		6 8		10	12	24	36	48/ES		T
	1	2	4 or 5	7 ±1	11 ±1	14 ±2	21 ±2	28 ±2	42 ±2	56 ±2	70 ±2	84 ±3	168 ±7	252 ±7	336 ±7		
Procedure		•		•				•	•				•	•			
SBT777101 administration	•																
Overnight stay/acute safety monitoring	•																
Patient self-temperature monitoring	•	•	•	•	•	•	•	•	•	•	•	•	•	•	•	•	•
Patient check-in (phone call, text etc) ^a		•	•	•													
Vital signs ^b	•	•	•	•	•	•	•	•	•	•	•	•	•	•	•	•	•
Adverse events ^c	•	•	•	•	•	•	•	•	•	•	•	•	•	•	•	•	•
Prior/Concomitant medications	•	•	•	•	•	•	•	•	•	•	•	•	•	•	•	•	•
Full physical exam				•				•		•					•		•
Directed physical exam	•	•	•		•	•	•		•		•	•	•	•		•	
Weight										•					•		•
12-lead triplicate ECG				•		•									•	•	•
Synovial biopsy for tissue								● ^{d,e}									•
Synovial fluid collection								●d,e				●d,e,f					•
Assessment of synovitis (clinical and/or ultrasound)								•				•					•
Urine pregnancy test	•											•	•		•		•
Lipid tests ^g															•		
Coagulation ^g													•		•		
Hematology ^g		•	•	•	•	•	•	•	•	•	•	•	•	•	•	•	•
Clinical chemistry ^g		•	•	•	•	•	•	•	•	•	•	•	•	•	•	•	•
Urinalysis ^g										•				•	•		•
Markers of inflammation h																•	
CRP		•		•		•	•	•	•	•	•	•	•	•	•	•	•
Joint count assessment (28 SJC/28 TJC)						•		•		•			•		•		•
Joint count assessment (66 SJC/68 TJC)												•					
Physician VAS						•		•		•		•	•		•		•
Subject VAS (global and assessment of pain)						•		•		•		•	•		•		•
HAQ-DI						•		•		•		•	•		•		•
FACIT-F													•		•		•
Blood samples for PK (ddPCR) i		•	•	•	•	•	•	•	•	•	•	•	•	•	•	•	•
Blood sample for cellular immunogenicity												•			•	•	•

FINAL Confidential

Version 1.0, 18-MAY-2022 Page 72 of 92

		Safety Follow Up				UV	ET										
Study Week			1			2	3	4	6	8	10	12	24	36	48/ES		
Study Day (visit window)	1	2	1 0 7 5	7	11	14	21	28	42	56	70	84	168	252	336		
	1	Z	4 or 5	±1	±1	±2	±2	±2	±2	±2	±2	±3	±7	±7	±7		
Procedure																	
Blood sample for ADA										•					•	•	•
Blood sample for exploratory inflammatory markers		•		•		•	•	•	•	•	•	•	•	•	•	•	•
Blood sample for ACPA/RF						•	•	•	•	•	•	•	•	•	•		•
Blood sample for VICM				•		•	•	•	•	•	•	•	•	•	•		•
Blood samples for exploratory biomarkers		•	•	•	•	•	•	•	•	•	•	•	•	•	•	•	•
Blood samples for RCL												•	•		•		

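### The Section 9.5 rule for results outside the quantitation limits runs opposite to its own example and leaves the size of the step undefined

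*Protocol*

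**What the plan says.** Section 9.5 (Data Handling Convention) sets one rule for "Laboratory data that are continuous in nature but are less than the lower limit of quantitation or above the upper limit of quantitation". Such values "will be imputed to the value of the lower or upper limit plus or minus one significant digit, respectively". The sentence ends with an example: "if the result of a continuous laboratory test is <10, a value of 9 will be assigned".

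Section 9.4.1 makes changes from baseline in clinical laboratory tests part of the primary endpoint. Section 9.7.2 summarizes those results and their changes by dose level and scheduled visit.

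PK has its own provisions. Section 9.4.2.1 derives Tmax, Cmax, AUC0-28 and Clast "by the evaluation of CAR transgene levels in peripheral blood", and Section 9.7.4 says that these parameters "will be determined using standard non-compartmental methods". Neither section gives a rule for samples below the limit. Section 9.5 neither names nor excludes transgene data.

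**The concern.** The sentence and its example cannot both be followed. With the word respectively, the lower limit pairs with plus and the upper limit with minus. A result known only to be under the lower limit then receives a value in the quantifiable range, and a result known to be over the upper limit is pulled down into it. In a safety study the second move understates the most extreme values. Two programmers, one following the words and one the example, would produce different laboratory datasets for a primary-endpoint summary.

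The phrase about one significant digit adds a second gap, because it does not say which digit moves.

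A secondary issue is scope. Section 7.2.6 places PK and PD sampling under the heading of laboratory assessments, and Section 7.3 lists "Labs for PK and immunogenicity". A reader could therefore carry the rule over to the transgene assay, where many samples may be below the limit.

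**Working it through.** **1. The plan's own figure.** Input from Section 9.5: lower limit L = 10, stated result 9.

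- As worded, one unit in the last digit: L + 1 = 10 + 1 = 11. This does not reproduce 9.
- Signs reversed: L − 1 = 10 − 1 = 9. This reproduces the example.
- Step in the leading digit: 10 + 10 = 20 or 10 − 10 = 0. Neither reproduces it.

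Only reversed signs with a step of one unit in the last written digit match. By the same logic, a result above an upper limit U should become U plus one step; the wording gives U minus one step.

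**2. Effect on one clinical laboratory result.** Wording and example differ by 11 − 9 = 2 units, or 2/10 = 20% of the limit. If baseline is a measured 10 and a later result is <10, the change is 11 − 10 = +1 under the wording and 9 − 10 = −1 under the example. The sign of the change reverses.

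**3. Conditional check: what if the rule were applied to transgene data?** The protocol gives neither the assay limit nor expected levels, so all of the following are assumptions: a limit of 10 units (borrowed from the example), mono-exponential decline from Day 2, and the pre-dose sample (Day −10 to −4, Appendix A) placed at time 0. Sampling follows the Appendix B row "Blood samples for PK (ddPCR" at Days 2, 4, 7, 11, 14, 21 and 28, that is 1, 3, 6, 10, 13, 20 and 27 days after infusion. AUC is by linear trapezoid, with below-limit samples set to 0 or to 9.

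A subject with no detectable transgene gets 9 × 27 = 243 (or 11 × 27 = 297 under the literal wording) instead of 0.

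One profile in full, Day 2 level 20 and half-life 2 days. Measured values are 20 and 10 at 1 and 3 days; the rest are below the limit.

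- Set to 0: (0+20)/2 + 2(20+10)/2 + 3(10+0)/2 = 10 + 30 + 15 = 55.
- Set to 9: (9+20)/2 + 30 + 3(10+9)/2 + 21 × 9 = 14.5 + 30 + 28.5 + 189 = 262.
- Increase: 262/55 − 1 = 376%.

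Increase in AUC0-28 from assigning 9 instead of 0:

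| Day 2 level | Half-life 2 d | 5 d | 10 d |
|---|---|---|---|
| 20 | 376% | 171% | 90% |
| 100 | 52% | 14% | 0.4% |
| 1,000 | 2.7% | 0.1% | <0.1% |
| 10,000 | 0.1% | <0.1% | <0.1% |

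The comparator matters. Stopping at the last quantifiable sample, the profile worked above gives 10 + 30 = 40 rather than 55. The table shows the range and is not an estimate for this product.

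Clast: for level 100 and half-life 5 days, the last quantifiable value is 18.9 at Day 14. If imputed values counted as measured, Clast would be 9 at Day 336. The same happens in every profile in the table, because all are below the limit by then.

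**The case against.** The strongest reply is that the example stands in the same sentence and shows the intended direction, so a careful programmer would assign 9 and this is an editorial slip. That is fair as to intent, and it makes the correction simple. It does not make the rule right as written, and the example covers only the lower limit; nothing illustrates the upper one.

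A reader might infer more than the documents support:

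- **That the rule governs transgene data and makes AUC0-28 and Clast wrong.** Section 9.5 speaks of laboratory data and a laboratory test. Section 7.3 lists clinical laboratory tests separately from PK samples. Section 9.7.4 sends the PK parameters to standard non-compartmental methods. Below-limit handling for PK is commonly left to an analysis plan, which is not at hand here. The scope is unstated; misapplication is not shown.
- **That the imputed area is the same at each dose and so flattens the dose-exposure relation by a constant.** It is not constant, because higher levels leave fewer samples below the limit. With a limit of 10, 9 assigned and a half-life of 5 days, the added area is 99, 36 and 4.5 at assumed Day 2 levels of 100, 300 and 900.
- **That cytokines need a particular substitute value, or that a zero would break a log transformation.** Section 9.5 plans means, medians, quartiles, standard deviations and ranges, with no log transformation. The choice of a substitute for cytokines is a preference.

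PK and PD endpoints are also exploratory, and escalation under Section 3.3 rests on DLTs and cumulative safety data.

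**Conclusion.** The contradiction is established from the text alone: the wording gives 11 where the example gives 9, and the step is not defined. It bears on laboratory change-from-baseline summaries within the primary safety endpoint. For a single result the difference is two steps (20% of the limit in the protocol's own example), enough to reverse the sign of a small change. How many results would be affected cannot be sized, since the protocol gives no quantitation limits for any test.

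The PK consequence is conditional. If the rule were applied to transgene data and imputed values were treated as measured, Clast would become an imputed constant whenever late samples are below the limit. The inflation of AUC0-28 would run from under 0.1% to 376% over the assumed profiles, and a subject with no detectable transgene would acquire a positive AUC. These figures rest on an assumed limit and assumed levels. They justify a sentence on scope, not a finding that the PK parameters are wrong.

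**What to change.** In Section 9.5, replace the rule so that a result below the lower limit takes the lower limit minus one unit in the last reported digit, and a result above the upper limit takes the upper limit plus one such unit. This matches the existing example; a second example for the upper limit would remove any doubt.

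Add that the rule applies to clinical laboratory tests and not to CAR transgene PK data, for which AUC0-28 and Clast follow the non-compartmental methods of Section 9.7.4, with Clast the last quantifiable value.

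The cost is two or three sentences in the protocol, carried into the analysis plan. No new data or procedures are needed.

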9.6. Demographic Data and Baseline Characteristics

Demographic and baseline measurements will be summarized using standard descriptive statistics. Demographic summaries will include but will not be limited to sex, race, ethnicity (Hispanic or non-Hispanic), age (at baseline), disease duration, RF and ACPA status. Baseline data will include a summary of screening body height and weight.

9.7. Safety Analysis

Safety analysis will be conducted based on the safety population. All safety data collected on or after the date that SBT777101 was first dosed will be summarized by dose level and overall. Descriptive statistics will be calculated for quantitative safety data and frequency counts will be compiled for classification of qualitative safety data. No inferential statistics will be done on safety assessments. In addition to safety analysis for SMC (see SMC charter for further details), a final safety analysis will occur after all enrolled patients have completed Week 48 visit. Full details for safety analysis will be provided in the SAP.

